5.2 Study Duration and Enrollment

Estimated duration for the main protocol (i.e., start of screening through to data analysis) is anticipated to be approximately 1-2 months. Subjects will be screened for eligibility within 15 days before the start of the study. The estimated time it will take for each individual participant to complete all study visits is less than or equal to 12 hours.

5.3 Justification of Dose

The dose chosen for this preliminary evaluation is primarily convenience-based for each component and is the amount that can adequately fit into one capsule.

5.4 End of Study Definition

Each subject will complete the study in a single calendar day. Each cohort will be considered completed when the total number of participants have completed their participation. The study will be considered completed when both cohorts have completed their participation and the data has been delivered and approved.

6. STUDY POPULATION

6.1 Inclusion Criteria

Individuals must meet all of the following criteria to be eligible to participate in this study:

- Willing to participate in the clinical trial
- Able and willing to provide informed consent
- Stable ileostomy (no revisions in the last 6 months)
- At least 19 years old
- Medically stable, but may be on medications for chronic conditions

6.2 Exclusion Criteria

Individuals will be excluded from this study if they meet any of the following criteria:

- Unable or unwilling to provide adequate informed consent
- Non-English speakers
- Clinically significant disease

- Women who are pregnant, intending to become pregnant, or breastfeeding
- Use of anti-diarrheal medicine
- Suffer gastroparesis
- Opioid use

6.3 Recruitment, Screening, and Enrollment

Healthy volunteers with mature ileostomies will be recruited by the site PI using advertising approved by the appropriate IRB/IEC. Volunteers who express interest in participating in the study will be asked to complete a pre-screen to assess general health status and basic eligibility. Potential volunteers determined to have an ileostomy and otherwise be generally healthy and meeting basic eligibility requirements will be scheduled for an in-person screening. Volunteers will be carefully screened on the details of the protocol and their time commitment.

7. STUDY SCHEDULE

7.1 Screening (within 15 days prior to study visit)

Volunteers will be screened for eligibility within 15 days before the study visit. Volunteers will be screened according to predefined inclusion criteria as described in [section 6.1](#). See [section 6.2](#) for a list of exclusion criteria. The following procedures will be performed at screening:

- Informed Consent
- Medical history, including existing medical conditions
- Record concomitant medications
- Physical exam
- Vital signs including heart rate, respiratory rate, seated blood pressure, and temperature
- Urine sample

7.2 Study Visit

Subjects will be asked to refrain from eating after 11 p.m. the night before arrival at study facility. The following procedures will be performed upon arrival:

- Assessment of inclusion/exclusion criteria
- Record concomitant medications
- Vital signs including heart rate, respiratory rate, seated blood pressure, and temperature
- Physical exam
- Urine sample
- Collect ileostomy fluid
- Administer study product

After IP is administered, the following procedures will be conducted every hour until study staff observe capsules or transit markers in ileostomy fluid collection:

- Collect ileostomy fluid for analysis as described in MOP
- Monitor for AEs and measure vital signs

After any transit markers is observed in the ileostomy fluid, study staff will repeat ileostomy fluid collection procedures hourly for a minimum of 4 additional hours or 12 hours total study participation, whichever comes first.

Participants can start eating 2 hours after dosing.

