1. PROTOCOL SUMMARY

1.1 Synopsis

Study Title: Exploratory study to assess delivery of LMN-201 components via enteric capsules in the gut of individuals with ileostomies	
Study Number: CDI01	
Phase of development: Phase 1	
Investigational Product: Components of LMN-201 (a cocktail consisting of a bacteriophage lysin specific for C. difficile organism and three VHH-derived proteins that bind and inhibit C. difficile toxin B, delivered in whole, spray-dried spirulina (Arthrospira platensis) biomass)	
Sponsor: Lumen Bioscience, Inc.	
Principal Investigator (PI): [name]	
Study Center: Coral Sea Clinical Research Institute	
Study Objectives (Primary):	
 To determine if enteric capsules are sufficient to deliver LMN-201 therapeutic proteins (VHH proteins and lysin) to the terminal ileum.
Study Objectives (Exploratory):	
 To document the presence of LMN-201 therapeutic proteins at the terminal ileum To determine variability between individuals in the quantity of LMN-201 therapeutic proteins at the terminal ileum
Subject Population	Adults aged 19 and above with mature ileostomy
Study Design	
This is a Phase 1, multi-site, open label, exploratory study of LMN-201 to evaluate the function of enteric capsules on drug release.
 
Eligible volunteers with mature ileostomies will be enrolled and sequentially assigned to treatment. After documentation of informed consent, subjects will be asked to swallow 4 enteric capsules of LMN-201 components, 1 enteric capsule containing ring-shaped transit markers, and 1 immediate release capsule containing tube-shaped transit markers. Every hour following ingestion, ileostomy fluid will be collected, weighed, filtered, and analyzed. The procedure will be repeated for 4 hours after capsules and/or transit markers are observed in the collected ileostomy fluid, or 12 hours after ingestion, whichever time is shorter.
 
In the first cohort, participants will receive only one of the LMN-201 VHH proteins administered in 3 enteric capsules as well as 1 enteric capsule containing lysin, 1 enteric capsule containing ring-shaped transit markers, and 1 immediate release capsule containing tube-shaped transit markers. In the second cohort, participants will receive 1 enteric capsule of each of the LMN-201 VHH proteins as well as 1 enteric capsule containing lysin, 1 enteric

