1.2 Schedule of Activities (SoA)

	Screening Visit	Study Visit		End of Study
		Dose	Follow up	
	Day -15 to 0	Hour 0	Hourly for 4 hours following observation of any transit markers or capsules, or for 12 hours, whichever time is shorter	
Study Procedures				
Consent	X			
Inclusion/exclusion criteria	X	X		
Medical History	X			
Physical Exam	X	X		
Vitals signs	X	X	X	
Urine Sample	X	X		
Study investigational product (IP) administered		X		
Collect ileostomy fluid for analysis ¹		X	X	
Record AEs			X	
Ship ileostomy fluid ¹				X

¹ See Manual of Procedures (MOP) for complete descriptions.

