9.2 Dosing Regimen

Subjects will receive individually encapsulated components of LMN-201, taken as four (4) capsules (500 mg biomass in each capsule), orally. In addition, they will receive an immediate release capsule containing ring-shaped transit markers and an enteric capsule containing tube-shaped transit markers to allow calculation of transit time and encapsulation dissolution visually.

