9.4 Dosage Form

LMN-201 ingredients are spray-dried spirulina biomass and trehalose. Individually encapsulated components of LMN-201 doses (500 mg) are packaged in size 00, white, opaque capsules (Capsugel, Morristown, NJ, US), Vcaps Enteric (first cohort) and Vcaps Plus (second cohort, if adapted). Vcaps Enteric capsules incorporate pH-controlled release technology designed to release encapsulated components at or before the terminal ileum. Vcaps Plus capsules are immediate release capsules designed to release encapsulated components in the stomach. No capsules contain any materials of human or animal origin.

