10.2 Documenting and Reporting AEs

All observed or volunteered AEs regardless of suspected causal relationship to the IP will be recorded on the AE page(s) of the case report form (CRF). The investigator must assess all AEs for seriousness, severity, and relation to IP.

The PI will follow all AEs, regardless of seriousness or severity, until the event or its sequelae resolve or stabilize at a level acceptable to the investigator.

The investigator is responsible for ensuring appropriate clinical management of all AEs until they are resolved or stabilized at a level acceptable to the investigator. Appropriate clinical management of AEs is at the discretion of the investigator.

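### Section 7.2 lists hourly AE checks and vital signs only until the first capsule or marker is seen, whereas the Schedule of Activities continues both for 4 more hours (12-hour maximum)

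*Protocol*

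**What the plan says.** Section 7.2 of the protocol describes the post-dose hours in two steps.

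- **Before the first sighting:** "After IP is administered, the following procedures will be conducted every hour until study staff observe capsules or transit markers in ileostomy fluid collection". Two bullets follow. One is ileostomy fluid collection; the other is "Monitor for AEs and measure vital signs".
- **After the first sighting:** "study staff will repeat ileostomy fluid collection procedures hourly for a minimum of 4 additional hours or 12 hours total study participation", whichever is earlier. AE monitoring and vital signs are not named in this step.

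The Schedule of Activities (section 1.2) has one follow-up column for the whole post-dose period, headed "Hourly for 4 hours following observation of any transit markers or capsules, or for 12 hours, whichever time is shorter". Vital signs, fluid collection and AE recording are all marked in it.

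Section 10.2 sets the general duty on adverse events: "All observed or volunteered AEs regardless of suspected causal relationship to the IP will be recorded". It has no cut-off at the first sighting, but it sets no hourly check and does not mention vital signs.

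**The concern.** The two texts give different end points for the scheduled post-dose safety checks. Section 11.3 evaluates safety from reported AEs, physical examination findings and vital signs. The physical examination is scheduled only at screening and on arrival before dosing (1.2, 7.1, 7.2). The hourly vital signs and AE checks are therefore the only scheduled safety assessments after the capsules are swallowed.

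The event that ends the 7.2 list is also not tied to release of the study product. Each subject takes one immediate-release marker capsule. Section 9.2 says "they will receive an immediate release capsule containing ring-shaped transit markers", while the synopsis has "1 immediate release capsule containing tube-shaped transit markers". Whichever shape is right, markers from that capsule can be the first thing seen. The LMN-201 capsules behave differently: "Vcaps Enteric capsules incorporate pH-controlled release technology designed to release encapsulated components at or before the terminal ileum". Some could still be in transit when the list ends. This last point does not apply to a second cohort switched to immediate-release capsules.

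At stake is the completeness of the vital-sign and active AE data behind a descriptive safety summary. If vital signs were absent after a sighting, it would be unclear whether they were missing or were never due.

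**Working it through.** The protocol states no figure on this point, so there is none to reproduce. The check compares the texts and then counts.

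**Step 1. What each text requires after the first sighting**

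| Item | Section 7.2, literal | Schedule of Activities (1.2) |
|---|---|---|
| Fluid collection | continues | continues |
| Vital signs | not named | continues |
| AE check | not named | continues |
| Event that ends the first step | capsule or marker | not applicable (single window) |
| Event that starts the further 4 hours | marker only | capsule or marker |

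The Schedule's footnote referring to the Manual of Procedures is attached only to collecting and shipping fluid, so it does not settle the vital-sign and AE rows. No other section restores scheduled vital signs after the sighting.

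**Step 2. The trigger gap within 7.2**

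If a capsule appears before any marker, the literal text ends the hourly list but does not yet start the continuation. Sections 1.1, 1.2 and 5.1 start the 4 hours from either a capsule or a marker, and section 8.1 has fluid collected hourly for the duration of the protocol. Fluid collection, and with it the primary endpoint, is therefore covered elsewhere.

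**Step 3. Size per subject**

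Inputs and assumptions:

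- t is the hour of first sighting. The protocol gives no transit data, so t is assumed over 1 to 12.
- The check at hour t itself is taken as done.
- The cap is 12 hours after dosing (1.1, 5.1; consistent with 1.2 and 8.1). The first hourly instruction in 7.2 has no cap of its own.

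Formulas:

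- Checks under literal 7.2 = t
- Checks under the Schedule = min(t + 4, 12)
- Checks omitted = min(t + 4, 12) − t = min(4, 12 − t)

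| t (hours) | Literal 7.2 | Schedule | Omitted | Share of Schedule |
|---|---|---|---|---|
| 1 | 1 | 5 | 4 | 80% |
| 4 | 4 | 8 | 4 | 50% |
| 6 | 6 | 10 | 4 | 40% |
| 8 | 8 | 12 | 4 | 33% |
| 9 | 9 | 12 | 3 | 25% |
| 10 | 10 | 12 | 2 | 17% |
| 11 | 11 | 12 | 1 | 8% |
| 12, or no sighting | 12 | 12 | 0 | 0% |

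The row t = 4 is singled out in the summary because 4 hours is the transit threshold in the adaptation rule of section 5.1. It is not an expected value.

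**The case against.** The strongest reply is that the Schedule already answers the question. It marks both safety items in the follow-up window. Section 7.2 never tells staff to stop them; it is only silent after the sighting. A site that reads both texts can satisfy both by following the Schedule, and nothing ranks 7.2 above it. The phrase about repeating collection procedures could also be stretched to cover the whole hourly list. Much of this stands: the Schedule is very probably the intent, and this is a drafting mismatch rather than two rival plans. But the post-sighting sentence names only fluid collection, which is a separate bullet from AE monitoring and vital signs, and the narrative section is one that staff may well work from.

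Four stronger readings are tempting, and the documents do not support them.

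- **A reader might infer that AE capture ends at the sighting.** Section 10.2 requires every observed or volunteered event to be recorded and followed, and staff still see the subject hourly to collect fluid. Only scheduled vital signs and active AE checks are in question.
- **A reader might multiply up to a trial-wide loss of 12 × 4 = 48 checks, or 9 × 4 = 36 with a second cohort of three, or cite the 80% at t = 1.** The totals need every subject to have a sighting by hour 8 and staff to disregard the Schedule each time. No transit data support any particular t.
- **A reader might infer that sites will diverge.** The protocol calls itself multi-site, but the synopsis names one study centre.
- **A reader might infer a serious safety gap because section 3.2 reports no GLP or formal toxicology studies.** The same section also cites a non-GLP mouse safety study, the recognised safety status of spirulina, and a completed Phase 1 trial of a related VHH product without significant AEs. The exposure here is a single oral administration.

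**Conclusion.** The inconsistency holds. Taken literally, section 7.2 omits min(4, 12 − t) scheduled hourly vital-sign and active AE checks per subject that the Schedule of Activities requires. That is 4 checks for any first sighting up to hour 8, falling to none at hour 12. Section 7.2 also uses different triggers for ending the first step and starting the second.

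The size rests on an assumed t, a 12-hour cap counted from dosing, and a site that follows 7.2 without consulting the Schedule. Importance is low: safety is descriptive, AE recording under 10.2 is unaffected, and neither the primary endpoint nor the sample size is touched. It is still worth correcting, because these checks are the only scheduled post-dose safety assessments feeding section 11.3.

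A reader might also infer that a later safety contact, such as a next-day query, is needed. The documents do not make its absence an error: section 5.4 has each subject complete the study in a single calendar day, and such a contact would be a change of design.

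**What to change.** Replace the two-step hourly instruction in section 7.2 with one statement:

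*Ileostomy fluid collection, AE monitoring and vital signs will be performed hourly after dosing until 4 hours after any capsule or transit marker is first observed, or until 12 hours after dosing, whichever comes first.*

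This aligns 7.2 with the Schedule, closes the trigger gap, and gives the hours before any sighting a cap. It makes two further edits that the amendment should declare. The 4 hours become a fixed period rather than a minimum, and the 12 hours run from dosing rather than counting total participation. Both bring 7.2 into line with sections 1.1, 1.2 and 5.1.

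The cost is one sentence submitted to the ethics board as an amendment. Against the Schedule it adds no visit, because the subject is already seen hourly for fluid collection. The added work is at most 4 sets of vital signs and AE checks per subject, all of which the Schedule already requires.

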7.3. Concomitant Medications

Concomitant medication use will be documented.

7.4 Early Termination

Subjects have the right to withdraw from the study at any time and for any reason. Subjects who withdraw their consent will not receive any further study drug but will be offered all follow-up safety assessments.

Subjects who withdraw from the study prior to treatment will be replaced per recruitment and enrollment processes outlined above in 6.3.

8. STUDY EVALUATIONS

8.1 Specimen Preparation, Handling, and Shipping

Ileostomy fluid is collected prior to the administration of study capsules, filtered, and aliquoted (either unadulterated or supplemented with purified proteins and protease inhibitor to use as a positive control). Once study capsules are administered, ileostomy content is collected hourly for the duration of the protocol (up to 12 hours). Upon collection, they are filtered, and the retained material is examined for the presence of intact capsules, capsule remnants, and transit markers. If these are observed, a photograph is taken to record the findings. The pH and volume of the filtrate are measured and recorded. Five 10 mL aliquots are prepared, supplemented with a protease inhibitor, and immediately flash frozen and stored at -80 °C until shipment. For shipment, one positive control, half of the pre-treatment samples, and 1 tube from each timepoint are assembled and transported on dry ice to Lumen Bioscience at the end of the study.

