Severe *C. difficile* colitis is associated with significant morbidity and mortality worldwide (Balsells et al., 2019). It causes an inflammatory colitis that can lead to diarrhea, abdominal pain, fever, and malaise. The biomolecules Lumen Bioscience has developed to treat and prevent *C. difficile* infection (CDI) need to be delivered, undigested, and in a fully functional form to the distal small bowel and large intestine to be effective. LMN-201 in its final form will be a 'cocktail' of several prophylactic proteins of two distinct classes: a bacteriophage lysin, and several engineered binding domain fragments of a single-domain camelid antibody (VHHs) delivered orally within whole, spray-dried spirulina biomass. The spirulina-bioencapsulated therapeutic proteins are delivered in vegetable-based, enteric delivery capsules of 500 mg total spirulina biomass. Such capsules are designed to release the drug product at or before the terminal ileum, the earliest point in the GI tract where conditions, including CDI, become established in most patients. These capsules are commonly used and procured from an industry provider (Vcaps Enteric, Capsugel, a Lonza company) and are covered by an active Drug Master File with the United States Food and Drug Administration (US FDA).

The first class of LMN-201 contains a single representative: a bacteriophage-derived lytic enzyme that is highly specific for degrading the *C. difficile* cell wall resulting in rapid hypotonic death (Wang, et al., 2015). These lytic enzymes, also called 'endolysins' or simply 'lysins', are a class of cell wall hydrolases with a narrow spectrum of activity. Research by the Fischetti Lab at Rockefeller University has shown that these enzymes efficiently kill all clinical isolate *C. difficile* strains tested to date, while leaving commensal bacteria undisturbed.

The second class consists of several VHHs that neutralize *C. difficile* exotoxins. Prior research has shown toxin B to be the primary driver of the disease pathology (Carter et al., 2015). Lumen Bioscience has developed three distinct VHHs that target different epitopes of toxin B.

As discussed further in the Investigator's Brochure, the safety and efficacy of LMN-201's therapeutic proteins were evaluated in a series of *in vitro* and *in vivo* studies. *In silico* assessments of target epitope homology to human and commensal bacterial proteomes showed a low risk of cross-reactivity. The

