4. OBJECTIVES AND ENDPOINTS

OBJECTIVES	ENDPOINTS
Primary	
To determine if enteric coating on components of LMN-201 is sufficient to deliver therapeutic proteins to the terminal ileum.	Presence or absence of capsules and/or transit markers in ileostomy fluid by visual observation

OBJECTIVES		ENDPOINTS	
Exploratory			
To document the presence of LMN-201 therapeutic proteins at the terminal ileum		Detect presence of LMN-201 therapeutic proteins (VHHs and lysin) in collected ileostomy fluid by EIA	
Exploratory			
To determine variability between individuals in the quantity of LMN-201 therapeutic proteins at the terminal ileum		Quantitate LMN-201 therapeutic proteins (VHHs and lysin) in collected ileostomy fluid by EIA	

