9. INVESTIGATIONAL PRODUCT

9.1 Investigational Product (IP)

The investigational product (IP), individually encapsulated components of LMN-201, will be supplied by Lumen Bioscience. LMN-201 is being developed to be a cocktail consisting of a bacteriophage lysin specific for degrading the *C. difficile* organism and three VHH-derived proteins designed to bind and inhibit *C. difficile* toxin B, delivered in whole, spray-dried spirulina biomass.

The LMN-201 drug substance is manufactured using four stable cell lines engineered to express the respective lysin and VHHs. The substance is manufactured under Current Good Manufacturing Practices (cGMP) using recombinant DNA processes and controls. The cells are cultured using chemically defined, animal-product-free basal medium under photoautotrophic growth conditions, using bicarbonate and CO₂ as the carbon source. After harvesting and rinsing with a dilute solution of trehalose, cells are spray dried to produce drug substance. The drug substance is fully tested against established specifications prior to release for further processing and use in clinical studies. Each strain contains a single

prophylactic protein, and the prophylactic protein 'cocktails' are generated by growing these strains separately, spray drying them separately, and finally dry-mixing the resulting powders together.

The LMN-201 drug product is manufactured at Lumen Bioscience's cGMP manufacturing facility in Seattle, Washington, US. The individually encapsulated components of drug substance are provided in pre-formulated capsules. The individually encapsulated components of LMN-201 drug product are tested for potency and purity defined by established specifications. Lumen Bioscience's cell banking protocols are designed to comply with ICH guideline Q5D for microbial cells. LMN-201 drug products and the tube-shaped transit markers will be filled into Vcaps Enteric intrinsically enteric vegetarian capsules size 00 (Capsugel). Ring-shaped transit markers will be provided in manufacturers non-enteric capsules (Medifactia AB).

Transit markers (Transit-Pellets™ Radiopaque Markers, manufactured by Medifactia AB) will also be provided by Lumen Bioscience.

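### The positive control in section 8.1 cannot show protein lost at the filter or left unreleased in spirulina biomass, so a low EIA result cannot by itself be read as digestion or failed delivery

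*Protocol*

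**What the plan says.** Section 8.1 treats the two kinds of sample differently.

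- **Pre-dose fluid** is "filtered, and aliquoted (either unadulterated or supplemented with purified proteins and protease inhibitor to use as a positive control". As written, the spike goes in at aliquoting, after the filter.
- **Post-dose fluid** is collected hourly. "Upon collection, they are filtered, and the retained material is examined for the presence of intact capsules, capsule remnants, and transit markers". Then "The pH and volume of the filtrate are measured and recorded", and after that "Five 10 mL aliquots are prepared, supplemented with a protease inhibitor, and immediately flash frozen and stored at -80 °C until shipment". Visual inspection is the only use stated for the retained material.
- **Shipment:** "For shipment, one positive control, half of the pre-treatment samples, and 1 tube from each timepoint are assembled". No sample containing biomass is listed as a control.

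The product takes a different form from the control protein. Section 3.1 states: "The spirulina-bioencapsulated therapeutic proteins are delivered in vegetable-based, enteric delivery capsules of 500 mg total spirulina biomass". Section 9.1 likewise describes the proteins as "delivered in whole, spray-dried spirulina biomass", and adds that each strain carries one protein and is grown and dried separately.

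The results that depend on the assay are the two exploratory endpoints in section 4: detection by EIA, and "Quantitate LMN-201 therapeutic proteins (VHHs and lysin) in collected ileostomy fluid by EIA". Section 5.1 also says that the first cohort is built to let digestion of the individual components be analysed. The primary endpoint in section 4 is visual observation of capsules and transit markers.

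**The concern.** A positive control supports a low result only for the steps that the control itself has been through. Here the control protein never meets the filter and is never inside a spirulina cell. Protein that reaches the stoma but is then trapped with retained material, or stays in the biomass and out of reach of the EIA, would lower the post-dose reading and leave the control looking good.

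This matters because EIA is the trial's only measurement of protein. The primary objective speaks of delivering therapeutic proteins to the terminal ileum, but its endpoint observes capsules and markers. Any statement about the protein itself, including how well each component survives digestion, rests on EIA values whose recovery from the dosed form is not checked in the plan as written.

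**Working it through.** The protocol states no figure on this point, so there is none to reproduce. The check follows the steps in order and then applies a simple recovery identity.

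**Steps side by side (section 8.1)**

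| Step | Positive control | Post-dose sample |
|---|---|---|
| Form of protein | Purified | In whole dried spirulina, or released from it |
| Passes the filter | No, added afterwards | Yes |
| Protease inhibitor | Added with the protein | Added after collection, filtration and aliquoting |
| Release from biomass needed | No | Yes, for protein still in cells; no step stated |
| Ileostomy fluid matrix, storage, shipping, EIA | Yes | Yes |

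**Recovery identity**

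Measured fraction = T × f × m, where

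- T is the true fraction of dose reaching the stoma;
- f is recovery through filtration and release from biomass;
- m is recovery through matrix, storage, shipping and EIA.

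The control estimates m and carries no information on f. The unspiked pre-dose aliquots show background signal and do not estimate f either.

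**Illustration (all values assumed; the protocol gives none)**

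Take a measured fraction of 0.20 and m = 0.95. Then T = 0.20 / (0.95 × f):

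- f = 1: T = 0.20 / 0.95 = 21%, a true loss of 79%
- f = 0.50: T = 0.20 / 0.475 = 42%
- f = 0.25: T = 0.20 / 0.2375 = 84%
- f = 0.21: T = 0.20 / 0.1995 = 100%, no true loss

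The same EIA value with the same good control thus fits anything from 79% loss to none.

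**How far f can depart from 1.** Suppose a share b of the protein at the stoma is still in biomass and is recovered at rate r, while released protein passes in full. Then f = 1 − b(1 − r). If all protein has been released (b = 0), f = 1 and the problem disappears. If none has (b = 1), f = r. The protocol gives neither b nor r.

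**Which comparisons are exposed**

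- *Between subjects, one component:* if f is the same in every subject it multiplies every value equally and cancels from the coefficient of variation. Relative variability is distorted only if f differs between subjects.
- *Between components:* for equal m, the measured ratio equals (T_A / T_B) × (f_A / f_B). With f of 0.50 for one strain and 0.25 for another, equal true delivery would appear as a 0.50 / 0.25 = 2-fold difference. Section 9.1 says the strains are grown and dried separately, so equal f cannot be taken for granted.

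**The case against.** The strongest reply is that the missing details belong elsewhere. The footnote to the schedule of activities (section 1.2) and section 7.2 send fluid handling to the Manual of Procedures, and a bioanalytical method normally sits outside a protocol. The retained material is searched for capsules, remnants and markers, all large objects, so the filter may be coarse enough for spirulina cells to pass. The laboratory may lyse the cells before assay. All of this stands, and it is why no bias can be asserted. It does not remove the point: section 8.1 itself fixes what the control is and when it is added, and a coarse filter would still leave release from biomass untested.

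A reader might go further and infer one of three things, none of which the protocol supports.

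- *That the control is worthless, or the only reference for the assay.* It does test matrix interference, storage, shipping and assay loss. Unspiked pre-dose aliquots are shipped too, and calibrators are simply not described. The protocol calls it a positive control, not a recovery control.
- *That EIA quantities are understated by some stated factor.* A recovery of 20% to 90% would give 1/0.20 = 5-fold to 1/0.90 = 1.1-fold understatement, but that range is pure assumption and its lower end is trivial.
- *That the trial's main result is at risk.* The primary endpoint is visual, and the adaptation rules in section 5.1 use intact capsules and transit time, not EIA. No passage commits the sponsor to reporting a low EIA value as digestion.

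It is also fair that no endpoint in section 4 ranks the components. The aim of analysing component digestion is nonetheless stated in section 5.1.

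**Conclusion.** The point holds in a limited form. On the text of section 8.1, the positive control can detect matrix interference and storage, shipping or assay loss, but not loss at filtration or incomplete release from biomass. A low post-dose EIA value with a good control therefore cannot, on its own, be attributed to digestion or failed delivery.

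The size of any bias is unknown: it depends on filter pore size, on extraction and on how much protein is still in biomass at the stoma. The 21% to 100% span above shows what the control leaves open and is not an estimate. The conclusion rests on reading section 8.1 in the order written and on no biomass control being described in the Manual of Procedures, which is not at hand. What is affected is confined to the exploratory EIA endpoints and the component-digestion comparison. It is worth settling before dosing, because a control made in each subject's own fresh pre-dose fluid cannot be added later.

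**What to change.** Keep the purified-protein spike for matrix and assay loss, and add a process control in section 8.1 and the Manual of Procedures:

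1. Set aside some unfiltered pre-dose fluid from the collection already made.
2. Add a weighed amount of same-lot biomass of the strains that subject receives (one VHH plus lysin in the first cohort, three VHHs plus lysin in the second), together with protease inhibitor.
3. Filter, aliquot, freeze, ship and assay it exactly as the post-dose samples.
4. Report post-dose quantities beside this recovery, and do not interpret low values as digestion without it.

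The sponsor would supply pre-weighed biomass vials separately from the single-dose packets, with their own accountability, since sections 9.8 and 13 restrict and track the product. Alternatively, a recovery run in the sponsor's laboratory with the same filter and blank unfiltered ileostomy fluid would serve. If the Manual of Procedures already contains such a control, a pointer in section 8.1 is enough.

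The cost is a little bench work, a small amount of drug substance and extra material accountability, with no added subject procedure. Two limits should be stated: fresh powder only approximates biomass that has passed through the gut, and because inhibitor is present from the start, this control does not measure breakdown between collection and the addition of inhibitor to the post-dose samples.
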